16.3.3.7. Change from baseline in YMRS total score over time

The YMRS total score and change from baseline will be summarized by time point for each treatment group. Change from baseline over time will be analyzed by the MMRM method described for primary endpoint with baseline YMRS total score as covariate (see [Section 16.1.3](#)).

Change from baseline over time will also be analyzed by the ANCOVA model described in [Section 16.1.5.1](#) with baseline YMRS total score as covariate.

Document:

Author:

Version Number:

V2.0

Version Date:

21MAY2020

Template No: CS_TP_BS016 Revision 4
Effective Date: 01Apr2016

Reference: CS_WI_BS005

17. SAFETY OUTCOMES

All outputs for safety outcomes will be based on the SAF population.

There will be no statistical comparisons between the treatment groups for safety data, unless otherwise specified within the relevant section.

17.1. PRETREATMENT AND ADVERSE EVENTS

Pretreatment events and AEs will be coded using the MedDRA central coding dictionary, Version 19.1 or higher.

Adverse events are untoward medical occurrences that occurred on or after the first dose of study medication, with a missing start date and a stop date on, or with both a missing start and stop date. Untoward medical occurrences that started between informed consent and prior to the first dose of study medication are pre-treatment events.

Any COVID-19 related Adverse Events and pretreatment events will be identified using a pre-defined search.

For the COVID-19 related terms, see Table 4 below.

Table 4. COVID-19 related adverse/pre-treatment event identification.

Verbatim text	Lower Level Term (LLT)	Preferred Term	Search
	Coronavirus test positive	Coronavirus test positive	Using LLT
Includes the term "COVID-19"	Virus test positive	Virus test positive	Using LLT and text "COVID-19" in the verbatim text.

Whenever available, the time information should be accounted for in the derivation of AEs vs. pretreatment events. In the case where time isn't available, untoward medical occurrences that started on or after the day of the first dose of study drug will be considered AEs; those that started before the day of the first dose of study drug will be considered pretreatment.

See [APPENDIX 2](#) for handling of partial dates for AEs. In the case where it is not possible to define an untoward medical occurrence as an AE or pretreatment event, it will be classified by the worst case, ie, AE.

An overall summary of the incidence of AEs within each of the categories described in the following sections will be provided as specified in the templates, including summary of COVID-19 related AEs and SAEs. This summary will also be repeated by region, race (category 2 in [Section 7.5](#)), sex, and age (< 55 and ≥ 55). The overall incidence summary will also be provided for AEs related to study drug.

Listings will be provided for all AEs, AEs leading to discontinuation of study drug, AEs leading to discontinuation from the study, serious adverse events (SAEs), and AEs leading to death. A listing for pretreatment events will also be presented. Any COVID-19 related AE will be flagged in the AE listings.

Document:

Author:

Version Number:

V2.0

Version Date:

21MAY2020

Template No: CS_TP_BS016 Revision 4
Effective Date: 01Apr2016

Reference: CS_WI_BS005

For incidence summaries, each subject will be counted only once within each SOC and PT. Adverse Events will be sorted alphabetically by SOC and then by decreasing frequency of PT within each SOC based on the All SEP-4199 treatment group. For the incidence summary table by SOC, High Level Term (HLT), and PT, each subject will be counted only once within each SOC, HLT and PT, and AEs will be sorted alphabetically by SOC and HLT, and then by decreasing frequency of PT within each SOC and HLT based on the All SEP-4199 group. If not otherwise specified, all summaries will present incidence (number of subjects and percentages) and number of events.

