12. SAFETY REPORTING

12.1. Definitions

12.1.1. Adverse Events

An AE is any untoward medical occurrence associated with the use of a drug in humans, whether or not considered drug related.

Untoward medical occurrences that occur between the time of signing the informed consent form (ICF) and drug administration are pre-treatment events. Those that occur after administration of study drug are considered AEs. Pre-treatment hospitalizations that occur in accordance with local clinical practice during the screening period (for wash-out from prior or concomitant medications) will not be considered as SAEs and do not need to be reported as such. Any untoward event that may occur during the hospitalization must be recorded as a pretreatment event. If hospitalization is prolonged by an untoward event, the event must be reported as an SAE.

An AE can, therefore, be any unfavorable and unintended sign (including an abnormal or clinically significant laboratory finding), symptom, or disease occurring after the administration of a medicinal (investigational) product, whether or not considered related to the medicinal (investigational) product. AEs may include the onset of new illness and the exacerbation of pre-existing conditions.

The Investigator should attempt to establish a diagnosis of the event based on signs, symptoms, and/or other clinical information. In such cases, the diagnosis should be documented as the AE and not the individual signs/symptoms.

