12.2. Objective Findings

Clinically significant abnormal objective findings (eg, clinical laboratory value, ECG value, and physical examination observation) will also be recorded as AEs.

When a clear diagnosis is available that explains the objective findings, this diagnosis will be recorded as the AE, and not the abnormal objective finding (eg, viral hepatitis will be recorded as the AE, not transaminase elevation). If a definite diagnosis is not available, then the sign (eg, clinically significant elevation of transaminase levels) or symptom (eg, abdominal pain) will be recorded as the AE.

The Investigator listed on the Form FDA 1572 (MD or DO) (or Sub-Investigator MD or DO as described on the delegation log) will review ECG and laboratory reports and initial and date on all pages, or other acceptable documentation process approved by the Sponsor. Laboratory test and ECG results will be reviewed by the Investigator as they become available. The Investigator must determine the clinical significance of all out-of-range lab values (except drug screens) and abnormal ECG results. Possibly drug-related or clinically relevant abnormal values of uncertain causality must be repeated. Any abnormal values that persist should be followed at the discretion of the Investigator. Any value outside the normal range will be flagged for the attention of the Investigator or appropriate designee at the study center. The Investigator or appropriate designee will indicate whether or not the value is of clinical significance. If the result of any test (or repeat test, if done) from the samples taken during Screening is indicated as clinically significant and is not covered by the inclusion criteria in [Section 8.1](#), the subject will not be allowed into the study. Additional testing during the study may be done if medically indicated. If a clinically significant abnormality is found in the samples taken after dosing, during the study, and/or at the Follow-Up Visit, this should be recorded as an AE and the subject will be followed until the test(s) has (have) normalized or stabilized.

If a subject experiences symptoms or ECG findings suggestive of an arrhythmia during the study, the subject should be evaluated by a cardiac specialist. If such an arrhythmia is detected during the study and is thought to be immediately life-threatening (eg, torsades de pointes [TdP]), the subject is to be treated immediately following the site’s standard emergency

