9. DISPOSITION AND WITHDRAWALS

All subjects who provide informed consent will be accounted for in this study.

Subject disposition will be presented for the screened subjects described by the randomized treatment group (where applicable) and overall for all subjects. The number and percentage of subjects who were screened, screen-failed, enrolled, randomized, randomized but not dosed, received study drug, completed or discontinued from the study treatment period, completed the treatment period and the follow-up visit, and completed the treatment period but not the follow-up visit will be presented. The number of subjects with non-missing change from baseline at Week 6 of MADRS total score and CGI-BP-S depression score will also be described. The number of subjects discontinued due to COVID-19 will be summarized and related reasons for discontinuations will be presented by relationship to COVID-

Document:

Author:

Version Number:

V2.0

Version Date:

21MAY2020

Template No: CS_TP_BS016 Revision 4
Effective Date: 01Apr2016

Reference: CS_WI_BS005

19.

With respect to the above, the following definitions apply:

- Screened Subjects: Any subject who signed the study specific informed consent and completed at least 1 study-related procedure.
- Enrolled Subjects: Any subject who was successfully screened and enrolled into the prerandomization period of the study.
- Randomized Subjects: Any subject who was randomized into the treatment period of the study and was assigned a randomization number.

COVID-19 related discontinuations are to be collected on the Disposition CRF page using the disposition reason = "Other" or "Adverse Event". For disposition reason = "Other", the sites are instructed to add the text "COVID-19" in the disposition reason detail. For disposition reason = "Adverse Event" due to COVID-19, the adverse event preferred term will be identified through a predefined MedDRA preferred term search as detailed in [Section 17.1](#).

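### The COVID-19 event search in SAP 17.1 covers only positive-test terms, so an illness recorded as a diagnosis, as the protocol asks, can go unflagged

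*SAP*

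**What the plan says.** SAP 17.1 sets one rule: "Any COVID-19 related Adverse Events and pretreatment events will be identified using a pre-defined search". Table 4 is that search, and it has two rows.

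- Row 1: lower level term and preferred term "Coronavirus test positive", searched by lower level term alone.
- Row 2: lower level term *Virus test positive*, with the instruction "Using LLT and text 'COVID-19' in the verbatim text". Both conditions must be met.

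The result feeds the COVID-19 AEs and SAEs in the overall incidence summary and a flag in the AE listings.

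SAP Section 9 uses the same search for part of the disposition summary. If the reason for discontinuation is Adverse Event, "the adverse event preferred term will be identified through a predefined MedDRA preferred term search as detailed in" Section 17.1. If the reason is Other, Table 4 is not used. For that reason "the sites are instructed to add the text" COVID-19 in the disposition detail.

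The protocol governs what the site writes down. Under Protocol 12.2, when a clear diagnosis explains an objective finding, "this diagnosis will be recorded as the AE, and not the abnormal objective finding". The fallback begins "If a definite diagnosis is not available, then the sign", and it allows the sign or symptom to be recorded instead. Protocol 12.1.1 takes the same line for clinical features: "the diagnosis should be documented as the AE and not the individual signs/symptoms".

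**The concern.** The search and the recording rule point in different directions. Table 4 looks for test results. The protocol tells sites to replace a test result with the diagnosis once there is a clear one, and the example in 12.2 (viral hepatitis in place of a transaminase rise) has the same pattern. A site that follows the protocol and enters a COVID-19 illness may thus produce a record that Table 4 does not select.

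At stake is the completeness of a small set of descriptive outputs: the COVID-19 AE and SAE summary, the listing flag, and the count of COVID-19 discontinuations that go through the Adverse Event reason. The SAP's modification history shows that the event identification was added in V2.0 to pick out these events. A reader of the report would take the count as complete.

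**Working it through.** No alpha, power, rate or sample size enters this point, and the plan gives no figure to reproduce. The check applies the two Table 4 rows and the two Section 9 routes to each way in which a COVID-19 case can reach the database.

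**Inputs.** Table 4 rows 1 and 2 (SAP 17.1); the two disposition routes (SAP 9); the recording rules (Protocol 12.1.1 and 12.2); coding in MedDRA 19.1 (SAP 3.7).

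| Case | How it is recorded | Selected? |
|---|---|---|
| 1 | Positive test as the event, coded to *Coronavirus test positive* | Yes, row 1 |
| 2 | Coded to *Virus test positive*, verbatim contains COVID-19 | Yes, row 2 |
| 3 | Coded to *Virus test positive*, verbatim uses another name such as SARS-CoV-2 | No, row 2 text condition fails |
| 4 | Diagnosis recorded (for example COVID-19 infection or pneumonia), coded to any other lower level term | No, even if the verbatim says COVID-19 |
| 5 | Discontinuation, reason Adverse Event, due to a case 3 or case 4 event | No, inherits the gap |
| 6 | Discontinuation, reason Other, with COVID-19 in the detail | Yes, by free text, independent of Table 4 |

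Case 4 is the central one. Protocol 12.1.1 and 12.2 lead to it whenever the diagnosis is clear. Row 2 shows that the authors saw a need for verbatim text, but it is used only to narrow one test term and never to select an event by itself. Case 1 remains the proper record when a positive test has no diagnosed illness behind it, because 12.2 then allows the finding to be the event.

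**Where the result is used.** Cases 3 and 4 lose the COVID-19 flag and their place in the COVID-19 AE and SAE summary. Case 5 is lost from the COVID-19 discontinuation count. Cases 3 and 4 still appear by system organ class and preferred term (SAP 17.1.1), in the discontinuation and SAE tables where they qualify (17.1.2, 17.1.3), and in the AE listings.

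**Where it is not used.** The primary analysis (SAP 16.1.3) does not refer to Table 4. The COVID-19 efficacy sensitivity analyses rest on remote-visit comments (16.1.4 and 16.1.4.4) and on the 11 March 2020 cutoff (16.1.4.5).

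**A second mismatch.** Section 9 calls the search a preferred term search, whereas Table 4 searches by lower level term and, in row 2, also by verbatim. Read literally, a search on preferred terms alone could count an Adverse Event discontinuation coded to *Virus test positive* with no mention of COVID-19. Table 4 would exclude it. The two sections can give different answers for the same subject.

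**The case against.** The strongest reply is that the coding step is not visible. SAP 3.7 states that MedDRA 19.1 was used, a lower version than the 20.1 that the protocol names as its minimum. How a COVID-19 verbatim was coded depends on that dictionary and on the coders' conventions, and neither is in the documents. Table 4 may simply mirror the convention in use, with illness reports placed under the two listed terms. V2.0 was also finalised after the blinded data review meeting and a review of draft outputs, so the authors may have fitted Table 4 to the events they had seen. This stands as a limit: no missed case is shown, and the number may be zero. It does not remove the gap in the written rule, because the SAP neither states such a convention nor makes the search depend on one.

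Four further points stand:

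- The diagnosis rule is conditional on a clear diagnosis, so some positive tests are properly recorded as tests and are found.
- Discontinuations with reason Other do not depend on Table 4.
- An unflagged event is not lost from the safety data, and SAP 17 plans no between-group tests for safety unless a section specifies them.
- A verbatim search with no review would also pick up entries such as anxiety about COVID-19. That is plausible here, since SAP 16.1.4 itself treats the pandemic as a psychosocial stressor. The remedy therefore needs a rule for what counts as a hit.

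**Conclusion.** As written, Table 4 does not flag a COVID-19 illness coded to any term other than its two positive-test terms, and the protocol's recording rules make such an entry the expected one when the diagnosis is clear. The COVID-19 AE and SAE summary, the listing flag and the count of Adverse Event discontinuations attributed to COVID-19 can therefore be too low. The error from unflagged illness runs only towards undercounting. Its size cannot be derived from the documents. It depends on two unknowns: whether any case was recorded as a diagnosis, and to which lower level term it was coded.

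A reader might infer that actual COVID-19 cases and the related discontinuations are missed in general, or that the missed cases are the more serious ones. The documents support neither reading. They show no coded case, they find discontinuations with reason Other by free text, and they contain nothing on the severity of cases recorded one way or the other. Nor is any efficacy result affected. This is a minor but genuine defect in a descriptive safety rule.

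**What to change.** Before unblinding:

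1. Add a row to Table 4 that selects any adverse or pretreatment event whose verbatim contains COVID, SARS-CoV-2 or coronavirus, whatever the lower level term.
2. Have the hits reviewed medically under blind, and drop those that are neither COVID-19 infection nor a positive test, such as anxiety about COVID-19.
3. Use the resulting list for discontinuations with reason Adverse Event in Section 9.
4. Reconcile the wording, so that Section 9 and Table 4 describe the same search (lower level term plus verbatim, not preferred term).

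The cost is one text search and a brief manual review of the hits. No new data are needed and no efficacy analysis changes. If every case was already coded to the two listed terms with matching text, the added row finds nothing new, and the count can then be reported as checked.

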17.1.1. ALL AEs

Adverse events will be presented by SOC and PT for AE incidence and number of events. A listing of all AEs will be presented.

An AE summary table by SOC, HLT, and PT will also be provided.

Adverse events reported by $\geq 2\%$ of subjects who received SEP-4199 and that occurred at greater incidence than in the placebo group will be summarized by SOC and PT.

Non-serious AEs occurring with a PT frequency exceeding 5% in any treatment group will be summarized by PT.

Adverse events will also be presented by maximum severity and by strongest relationship to the study drug as specified in the sections below.

17.1.1.1. Severity

Severity is classified as mild/ moderate/severe (increasing severity). Adverse events with a missing severity will be summarized as severe. If a subject reports an AE more than once within the same SOC/PT, the AE with the worst severity will be used in the corresponding severity summaries. For this summary, AEs will be presented by SOC and PT.

17.1.1.2. Relationship to Study Drug

Relationship to study drug, as indicated by the investigator, is classed as “not related”/ “possible”/ “probable”/ “definite” (increasing strength of relationship). A “related” AE is defined as an AE with a relationship to the study drug of “possible”, “probable” or “definite”. A “not related” AE is defined as an AE with a relationship to the study drug of “not related”. Adverse events with a missing relationship to the study drug will be regarded as “related” to the study drug. If a subject reports the same AE more than once within the same SOC/PT, the AE with the strongest relationship to study drug will be used in the corresponding relationship summaries. For this summary, AEs will be presented in 2 categories, related and not related, by SOC and PT.

17.1.2. AEs LEADING TO DISCONTINUATION FROM STUDY TREATMENT PERIOD

Adverse events leading to discontinuation from the study treatment period are AEs with “Caused Study Discontinuation” = “Yes” on the AE CRF page for subjects with reason for discontinuation as AE on the Study Disposition CRF page or AE action taken=“Drug Withdrawn”. A summary of AEs leading to

Document:

Author:

Version Number:

V2.0

Version Date:

21MAY2020

Template No: CS_TP_BS016 Revision 4
Effective Date: 01Apr2016

Reference: CS_WI_BS005

discontinuation from the study treatment period by SOC and PT will be presented. A listing of AEs leading to discontinuation from the study treatment period will be presented.

17.1.3. SERIOUS ADVERSE EVENTS

Serious AEs are those AEs recorded as “Serious” on the AE CRF page. Summaries of SAEs by SOC and PT will be prepared. Related SAEs will be summarized. A listing of SAEs will be presented.

17.1.4. ADVERSE EVENTS LEADING TO DEATH

AEs leading to death are those AEs which are recorded as having an outcome of “Fatal” on the AE CRF page. A summary of AEs leading to death by SOC and PT will be prepared. Related AEs leading to death will be summarized. Overall deaths resulting from all causes will also be presented. A listing of deaths will be presented.

17.1.5. ADVERSE EVENTS BY SUBGROUP

As stated above, the overall incidence summary table and the AEs by SOC and PT summary table will also be presented by the subgroups of region as appropriate, race (category 2 in [Section 7.5](#)), gender, and age.

17.2. LABORATORY EVALUATIONS

All summaries will be based on the SAF population. Laboratory data to be reported for this study include Hematology, Serum Chemistry (including lipid panel and thyroid panel), Urinalysis, Urine drug screening, Hemoglobin (HbA1c), serum follicle stimulating hormone (FSH), Serum Prolactin, Serology, Serum Insulin, C-Reactive Protein (CRP), and urine pregnancy test. A list of laboratory assessments to be included in the outputs is included in section 21 of the CSP. Urine drug screening, serum FSH, serology, and urine pregnancy test will only be listed.

Presentations will use international system of units (SI).

Quantitative laboratory measurements reported as “< X”, ie, below the lower limit of quantification (BLQ), or “> X”, ie, above the upper limit of quantification (ULQ), will be converted to X for the purpose of quantitative summaries, but will be presented as recorded, ie, as “< X” or “> X” in listings.

The following summaries will be provided for laboratory data:

- By-visit summary of observed values and changes from baseline for continuous data in hematology, chemistry, and urinalysis.
- By visit summary of the number and percentage of subjects in each outcome category for categorical data in urinalysis (if applicable).

Document:

Author:

Version Number:
Version Date:

V2.0

21MAY2020

Template No: CS_TP_BS016 Revision 4
Effective Date: 01Apr2016

Reference: CS_WI_BS005

- Shift in laboratory results (chemistry, hematology, urinalysis) from baseline to Week 6 according to the reference range criteria. The normal reference ranges from the central laboratory will be used to determine whether the laboratory test value is below, within, or above the normal range. Urinalysis will be presented as normal or abnormal (including low, high, abnormal) in the shift table.
- By planned visit (after mapping of the ET visit) and overall (including unscheduled visits) summary of markedly abnormal postbaseline value (MAPLV, see [Section 17.2.1](#) and [APPENDIX 5](#)). Subjects will be represented in the count of a particular MAPLV (potentially clinically significant [PCS] low or high) if they have experienced that MAPLV at least once postbaseline, regardless of baseline value. The number and percentage of subjects with MAPLV will be presented by treatment group.
- Shift in markedly abnormal laboratory results from baseline to postbaseline according to the markedly abnormal criteria as presented in [APPENDIX 5](#).
- Serum prolactin results will be summarized overall and separately by gender. Glucose, insulin, and lipid panel results, along with a derived variable for homeostasis model assessment of insulin resistance (HOMA-IR) will be summarized for fasting only and overall (fasting, non-fasting, or fasting status unknown combined) status. HOMA-IR will be derived based on glucose and insulin results as: $HOMA-IR = \text{Glucose (mg/dL)} \times \text{Insulin (mU/L)} / 405$ ([Matthews 1985](#)). HbA1c will also be summarized.
- The change from baseline values at Week 6 for selected laboratory parameters will be evaluated using a nonparametric rank ANCOVA analysis with adjustments for the corresponding baseline values for comparison between each SEP-4199 group and placebo. Using the regression residuals from the rank ANCOVA analysis as scores, the Mantel-Haenszel row mean scores test will be used to compare between the treatment groups. This analysis will be conducted for CRP, Glucose (Fasting and Overall), Insulin (Fasting and Overall), HOMA-IR (Fasting and Overall), Cholesterol Total (Fasting and overall), HDL (Fasting and Overall), LDL (Fasting and Overall), Triglycerides (Fasting and Overall), Prolactin (Overall, Male, and Female), and HbA1c (Fraction of 1).

All laboratory data will be provided in data listings, with the values outside the reference ranges flagged.

